11.5 End of Treatment Visit

The following assessments will occur approximately 30 days (30 ± 7 days) after the last administration of study drug or immediately before the administration of another anticancer drug, whichever takes place first:

- Record any RBC, whole blood and platelet transfusions that were received since the last study visit.
- Record concomitant medications
- Assessment of AEs
- Assess ECOG performance status.
- Record subject weight
- Collect vital signs (heart rate, blood pressure, temperature)
- Complete physical examination
- Perform urine or serum pregnancy test for females of child-bearing potential only
- Perform serum chemistry laboratory tests (AST, ALT, total bilirubin, creatinine, BUN, potassium and calcium). Subjects are not required to be fasting.

- Perform hematology tests: hemoglobin, reticulocytes, platelets, WBCs, neutrophils, neutrophil precursors (promyelocytes, myelocytes, metamyelocytes, band neutrophils), monocytes, lymphocytes and blasts
- Perform coagulation tests (APTT, PT/INR)
- Perform disease and response assessment:
 - O Perform bone marrow aspirate for disease assessment, cytogenetic assessment and NGS oncogene panel as part of the End of Treatment visit if the visit occurs during the first 9 months from the start of the subject's participation in the study. Thereafter, bone marrow evaluations will occur during End of Treatment visit in accordance with institutional standard practice. If the bone marrow aspirate is inadequate, a bone marrow biopsy should be performed. If on this bone marrow sample, a CR or PR is observed, a bone marrow aspirate with cytogenetic assessment must be repeated 1 month later.
 - Investigator review of subject RBC transfusions, hematology and bone marrow evaluation (if available) for completion of response assessment.

• Conduct drug accountability on the returned empty bottles and unused medications.

11.6 Post Treatment Follow up

11.6.1 Subjects who Terminate Treatment for Reasons other than Death or Disease Progression

Subjects who terminated treatment for reasons other than death or disease progression will be assessed at regular intervals for disease progression and leukemic transformation.

The assessments to be conducted at each monthly visit are:

• Perform hematology tests (hemoglobin, platelets, WBCs, neutrophils, neutrophil precursors, monocytes, lymphocytes and blasts)

The assessments to be conducted at each approximately every 12 weeks visit are

- Record any RBC, whole blood and platelet transfusions that were received since the last study visit.
- Perform disease and response assessment:

- Perform bone marrow aspirate as part of the assessments if post-treatment follow-up visit is conducted during the first 9 months from the start of the subject's participation in the study. Thereafter, bone marrow evaluations will occur during post-treatment follow-up visits in accordance with institutional standard practice. If the bone marrow aspirate is inadequate, a bone marrow biopsy should be performed. If on this bone marrow sample, a CR or PR is observed, a bone marrow aspirate with cytogenetic assessment must be repeated 1 month later.
- o Investigator review of subject RBC transfusions, hematology and bone marrow evaluation (if available) for completion of response assessment.
- Assessments of AEs and concomitant medications may also be conducted if AEs were not resolved at the time of the End of Treatment visit.

11.6.2 Follow Up after Disease Progression

Upon disease progression, all subjects in the study will be followed approximately every 12 weeks for survival and the use of subsequent therapy until either death or 12 months after accrual of the study cohort has been completed, whichever occurs first. Information on survival and subsequent anticancer therapy may be collected by phone.

12 STATISTICAL METHODS

This section outlines the statistical analysis strategy and procedures for the study. Specific details of the primary and key secondary analyses will be provided in the Statistical Analysis Plan (SAP). If, after the study has begun, but prior to the final analysis, important changes are made to the protocol that affect principal features of the primary or key secondary analyses, then the protocol and/or SAP will be amended, as appropriate. Any other changes made to the planned analyses after the protocol and SAP have been finalized, along with an explanation as to when and why they occurred, will be listed in the Clinical Study Report (CSR) for the study. Post hoc exploratory analyses will be clearly identified in the CSR.

12.1 Populations

12.1.1 Efficacy Analysis

The full analysis set (FAS) will serve as the primary population for the analysis of ORR and other efficacy-related data. Prior to Amendment 2 (version 20 Dec 2016), other subjects were enrolled into the trial using a different dose regimen. Also, for inclusion in the FAS, subjects must meet all Amendment 3 inclusion criteria. For the purposes of the primary analysis (advancement from stage 1 to stage 2 and overall analysis for each dose regimen cohort), those subjects will not be included. The excluded subject data will be summarized separately in the reporting of the study.

Therefore, subjects will be excluded from the FAS for the following reasons:

- Did not meet eligibility criteria as outlined in Amendment 3 (version 09 Jul 2017)
- Failure to receive at least one dose of tipifarnib
- No post-baseline endpoint data subsequent to at least 1 dose of study drug
- Enrolled prior to Amendment 2 (version 20 Dec 2016)

A supportive analysis may be performed on the Per-Protocol population which excludes subjects due to important deviations from the protocol that may substantially affect the results of the primary analysis, such as not taking at least 80% of the intended dose in cycle 1. The final determination on protocol violations, and thereby the composition of the Per-Protocol population, will be made prior to locking the clinical database and final analysis and will be documented in a separate memorandum.

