8.2 Subject Identification and Replacement of Subjects

Each subject will be assigned a unique subject identifier. This unique identifier will be on all case report form (CRF) pages. Subjects who do not receive at least one dose of tipifarnib will be replaced.

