10.1 Efficacy Variables

Hematologic assessments, including peripheral blood evaluations and review of transfusion requirements, will be performed at screening and at least monthly until disease progression. Disease assessments will also be performed at screening and at least once every approximately 12 weeks starting at the end of cycle 3. As part of the disease assessment at screening and during Cycles 3, 6 and 9, bone marrow evaluation will be performed. Thereafter, bone marrow evaluations will occur during disease assessments in accordance with institutional standard practice. Additional hematologic or disease assessments may be conducted if deemed necessary by the Investigator.

Disease response assessment will be performed by the Investigator according to the MDS IWG criteria (Table 9 and Table 10).

Determination of RBC TI (secondary endpoint) will be assessed by the investigator through the review of subject transfusion requirements and hemoglobin levels. RBC TI will be defined as the absence of the intravenous infusion of any RBC transfusion during any consecutive "rolling" 56 days during the treatment period, i.e. days 1 to 56, days 2 to 57, days 3 to 58, etc. and $a \ge 1$ g/dL increase in hemoglobin level.

Upon disease progression, all subjects in the study cohort will be followed approximately every 12 weeks for survival and the use of subsequent therapy until either death or 12 months after accrual of the study cohort has been completed, whichever occurs first. Information on survival and subsequent anticancer therapy may be collected by phone.

Subjects who terminate treatment for reasons other than death or disease progression will be assessed at regular intervals for disease progression (approximately every 12 weeks) and leukemic transformation (monthly blood counts). Disease assessments performed during the first 9 months from the start of the subject's participation in the study will include bone marrow evaluation. Thereafter, bone marrow evaluations will occur during disease assessments in accordance with institutional standard practice. These assessments will continue until disease progression, withdrawal of subject's consent to study procedures or initiation of another anticancer therapy.

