Progression free survival will be defined as the time (in months) from enrollment to either first observation of progressive disease or occurrence of death due to any cause within 1 year (approximately 4 time intervals for disease assessments) of either first administration of tipifarnib or the last disease assessment. Similarly, survival will be defined as the time (in months) from enrollment to occurrence of death due to any cause within 1 year (approximately 4 time intervals for disease assessments) of either first administration of tipifarnib or the last disease assessment

Determination of RBC TI will be assessed by the Investigator through the review of subject transfusion requirements and hemoglobin levels. RBC TI will be defined as the absence of the intravenous infusion of any RBC transfusion during any consecutive "rolling" 56 days during the treatment period, i.e. days 1 to 56, days 2 to 57, days 3 to 58, etc. and a \geq 1 g/dL increase in hemoglobin level. The rise in the hemoglobin concentration in subjects who no longer require transfusions will be calculated as the difference between the maximum hemoglobin concentration and the minimum pre-transfusion value during the 12 weeks before enrollment in the study.

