A two-stage study design was selected in order to minimize the number of study subjects treated if tipifarnib were considered not sufficiently efficacious to grant further development in this subject population. This design is intended to allow the termination of accrual in case of unacceptably low efficacy as measured by ORR and will be evaluated in a FAS basis.

In the first stage, 22 eligible subjects will be enrolled and randomized in to one of two dose regimen cohorts (11 subjects per cohort). If two or more responses are observed in a given dose regimen cohort, 7 additional study subjects will be enrolled. Each dose regimen cohort is designed to test the null hypothesis of ORR rate less than 10% vs alternative hypothesis of ORR rate at least 30% and will be evaluated independently. At the completion of the study, treatment will be considered of further interest if 4 or more subjects in the 18 subject dose regimen cohort achieve a response, i.e. the true ORR is higher than 10%.

To determine the total trial size, a response of interest of 30% is assumed. This design provides 80% power to detect a difference between 10% and 30% RBC TI rate at one-sided significance level of 0.087. Using this design, the probability of terminating each stratum at the end of stage 1 if the true rate is 10% is 0.697 while the probability of terminating each stratum at the end of stage 1 if the true rate is 30% is 0.113.

The performance characteristics of this approach are shown in Table 7.

Table 6: Performance characteristics for sample size determination

	Probability to conclude TRUE rate > 0.10 if TRUE underlying RBC TI response rate is as indicated		
TRUE Rate>	0.1	0.3	0.4
N=11	0.09	0.69	0.88
N=18	0.1	0.83	0.97
N=25	0.1	0.91	0.99
N=32	0.09	0.95	>0.99

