7.5. Handling of Dropouts or Missing Data

Where individual data points are missing because of insufficient samples, dropouts, or other reasons, the data will be analyzed based on reduced denominators. For survival analysis, dropouts without confirming events will be treated as censored.

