9.1. Primary Efficacy Analyses

The objective response rate will be estimated and includes the following response types CR, PR, marrow CR and HI according to the MDS IWG criteria (Table 8 and Table 9 in the study protocol). The estimate of the ORR will be calculated based on the maximum likelihood estimator (i.e., crude proportion of subjects whose best overall response is CR, PR, marrow CR or HI). The estimate of the ORR will be accompanied by a 2-sided 95% exact binomial confidence interval.

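### Dosed, eligible subjects with no post-baseline endpoint data (a term left undefined) leave the ORR denominator instead of counting as non-responders, so the reported ORR and its exact CI can only be equal to or higher than in all treated eligible subjects; the effect is small and the go/no-go rule does not move

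*Protocol*

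**What the plan says.** - **Population.** Protocol 12.1.1 and SAP 6 name the FAS as the primary population for ORR and list four reasons for exclusion. The third, identical in both documents, is "No post-baseline endpoint data subsequent to at least 1 dose of study drug". The available text of neither document says what endpoint data means.
- **Estimator.** Protocol 12.2.1 and SAP 9.1 estimate ORR as the crude proportion whose best response is CR, PR, marrow CR or HI. SAP 9.1 adds: "The estimate of the ORR will be accompanied by a 2-sided 95% exact binomial confidence interval".
- **Missing data.** Under SAP 7.5, where data points are missing through dropout or other causes, "the data will be analyzed based on reduced denominators". No section counts a treated subject without an assessment as a non-responder.
- **Decision rule.** Each cohort continues with at least 2 responders in stage 1 (11 subjects) and succeeds with at least 4 in 18. The sample size section (Protocol 12.4, SAP 5) says that efficacy "will be evaluated in a FAS basis".
- **Replacement.** The only rule is in Protocol 8.2: "Subjects who do not receive at least one dose of tipifarnib will be replaced".

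**The concern.** A recorded responder always has post-baseline endpoint data. The exclusion can therefore remove only subjects with no recorded response, and every removal shrinks the denominator while the numerator stays fixed. In a cohort of 18, each subject is worth more than a percentage point.

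The missing definition adds to this. Two analysts could settle the FAS differently and report different primary ORRs from the same data. The trial is open label with investigator-assessed response, and the memorandum due before database lock (Protocol 12.1.1, SAP 6) fixes only the Per-Protocol set. The choice could thus be made with responses already known. At stake is the headline estimate and its interval.

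**Working it through.** **1. The plan's own design figures.** Continue if X1 ≥ 2 of 11; succeed if the total is ≥ 4 of 18.

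P(success) = Σ over x ≥ 2 of P(X1 = x; 11, p) × P(X2 ≥ 4 − x; 7, p)

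At p = 0.10:
- x = 2: 0.2131 × 0.1497 = 0.0319
- x = 3: 0.0710 × 0.5217 = 0.0371
- x ≥ 4: 0.0185
- sum: 0.0875 (stated 0.087)

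At p = 0.30 the sum is 0.800 (stated 80%). The probabilities of stopping after stage 1 are 0.697 and 0.113, as stated.

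**2. Direction.** With x responders, n treated eligible subjects and k dropped, x/(n − k) ≥ x/n. A numerical check over n = 2 to 39 found no case in which the estimate or either exact limit fell. With x = 0, the estimate and lower limit stay at 0 and only the upper limit rises.

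**3. Size** (Clopper-Pearson 95% limits):

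| Responders | None dropped | One dropped | Two dropped |
|---|---|---|---|
| 4 | 4/18 = 22.2% (6.4 to 47.6) | 4/17 = 23.5% (6.8 to 49.9) | 4/16 = 25.0% (7.3 to 52.4) |
| 5 | 5/18 = 27.8% (9.7 to 53.5) | 5/17 = 29.4% (10.3 to 56.0) | 5/16 = 31.2% (11.0 to 58.7) |

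At 4 responders the shifts are 1.3 and 2.8 points, against an interval 47.6 − 6.4 = 41.2 points wide. At 5 responders, one drop carries the lower limit across the 10% null value.

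**4. Who would be dropped.**
- *Broad reading.* Protocol 10.1 states: "Hematologic assessments, including peripheral blood evaluations and review of transfusion requirements, will be performed at screening and at least monthly until disease progression". HI is itself part of ORR, and the PFS definition in Protocol 12.2.1 takes in "either first observation of progressive disease or occurrence of death due to any cause". One post-dose blood count, a progression or a death then keeps a subject in the FAS, and only those lost before any post-dose record go. This assumes that SAP 7.5 is not then used to remove FAS members who have no response assessment.
- *Narrow reading* (a response assessment is required). The first scheduled one is at Cycle 3 Day 22, which is day 28 + 28 + 22 = 78. Subjects lost before then go too, unless they have an End of Treatment visit, which includes "Investigator review of subject RBC transfusions, hematology and bone marrow evaluation (if available) for completion of response assessment".

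**5. How often.** The documents give no dropout assumption for this trial. As a rough proxy, Protocol 5.5.3 gives treated and evaluable numbers for three MDS studies:
- 21 − 20 = 1 of 21 (4.8%)
- 28 − 27 = 1 of 28 (3.6%)
- 63 − 61 = 2 of 63 (3.2%)
- pooled: 4/112 = 3.6%

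Assuming independent subjects, P(at least 1 of 18 dropped) = 1 − (1 − f)^18:
- f = 2/63: 0.44
- f = 4/112: 0.48
- f = 1/21: 0.58

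The fourth study (82 patients) uses 82 as its denominator but gives no non-evaluable count. It describes 26 responders and 37 with stable disease, leaving 82 − 63 = 19 undescribed, so it is left out and not scored as zero.

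**6. Go/no-go.** The thresholds are counts of responders, and dropping non-responders does not change the count. With 11 and 18 dosed eligible subjects, the false-go rate stays at 0.0875 and power at 0.800. If cohorts were instead refilled to 11 and 18 FAS subjects, a true 10% rate per dosed subject would become 0.10/(1 − f) per FAS subject. That is 0.1033 at f = 2/63 and 0.1050 at f = 1/21, giving false-go rates of 0.096 and 0.101.

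**The case against.** The strongest reply is that the exclusion may be almost empty. The FAS serves ORR and other efficacy data, so endpoint data most naturally means any efficacy record, and monthly counts begin to accrue by Cycle 2 Day 1. Protocol 8.4 also asks for every effort to complete the End of Treatment tests. This stands as the better reading, and it is why the point is small. It is not written down, however, and the exclusion then serves little purpose in the FAS.

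A reader might infer that the reported ORR is biased upward outright. The documents do not support that. A subject lost before any record has an unknown response. If loss were unrelated to response, the reduced denominator would be unbiased and counting non-responders would pull ORR down. The one-way direction holds only against the convention that all treated eligible subjects count.

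A reader might also infer that the false-go rate is inflated, because evaluation is on a FAS basis against an 18-subject cohort. That needs refilling to FAS size, which no section provides for; Protocol 8.2 replaces only never-dosed subjects. Nor does the lower limit crossing 10% matter to the decision, since the rule does not use the interval.

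Finally, the reporting helps. SAP 8.1 lists population assignment, and SAP 8.3 summarizes demographics for both the all-treated set and the FAS, so a reader could largely recompute. The headline figure would still rest on the reduced denominator. Protocol 12.1.1 promises a separate summary of excluded subjects, but that sentence follows the amendment-related exclusions and may not cover this group.

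**Conclusion.** The point holds as a limited one. Relative to all treated eligible subjects, the ORR and its exact limits can only be equal or higher: by 1.3 points for one drop at 4 responders in 18, and by about nothing if endpoint data is read broadly. The chance of 44% to 58% (48% pooled) of at least one drop in a full cohort is an assumption-based range. It rests on three earlier studies, on independence, and on non-evaluable there meaning roughly what this exclusion means, which the documents do not establish. The go/no-go rule and its error rates are unchanged provided the 11 and 18 are dosed eligible subjects. Low priority.

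**What to change.** 1. Protocol 12.1.1 and SAP 6: delete the third exclusion from the FAS. It may be kept for the Per-Protocol set, with endpoint data defined there.
2. SAP 7.5, add: *For ORR, treated subjects who meet the other FAS criteria but have no post-baseline response assessment are counted as non-responders, remain in the denominator of the ORR and its CI, and are not replaced.*

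The no-replacement clause is limited to subjects who meet the other FAS criteria, so it says nothing about dosed subjects who are ineligible or were enrolled before the relevant amendment. It also closes off the reading in which cohorts are refilled to FAS size.

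Cost: wording in three places, with no extra subjects and no change to the two-stage rule. The reported ORR may come out slightly lower.

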12.1.2 Safety Analysis

The All Subjects as Treated (ASaT) population will be used for the analysis of safety data. The ASaT population consists of all enrolled subjects who receive at least one dose of tipifarnib. At least one laboratory or vital sign measurement obtained subsequent to at least one dose of study drug is required for inclusion in the analysis of a specific safety parameter. To assess change from baseline, a baseline measurement is also required.

12.2 Endpoints

12.2.1 Efficacy

Disease response assessment will be performed by the Investigator according to the MDS IWG criteria (Table 9 and Table 10).

For the evaluation of the primary endpoint (i.e. ORR) to determine advancement to the second stage of the study (i.e. enrollment of 7 additional subjects in the dose regimen cohort) and overall outcome of the study, each dose regimen cohort will be evaluated independently.

Transfusion independence and disease response will be summarized descriptively per dose regimen cohort and overall.

The objective response rate will be estimated and includes the following response types: CR, PR, marrow CR and HI according to the MDS IWG criteria (Table 9 and Table 10). The estimate of the objective response rate will be calculated based on the maximum likelihood estimator (i.e., crude proportion of subjects whose best overall response is CR, PR, marrow CR or HI). The estimate of the objective response rate will be accompanied by 2-sided 95% exact binomial confidence intervals.

The duration of objective response will be calculated for subjects who achieve CR, PR, marrow CR or HI. For such subjects, the duration of objective response is defined as the number of days from the start date of response (whichever response is achieved first) to the first date that progressive disease is objectively documented. Disease progression will be determined by the Investigator using MDS IWG criteria (Table 10). The duration of objective response will be right-censored for subjects who achieve a response and meet 1 of the following conditions: 1) non-protocol anticancer treatment started before documentation of disease progression, 2) death or documented disease progression after more than 1 missed disease assessment visit, or 3) alive and does not have documentation of disease progression before a data analysis cutoff date.

The duration of objective response will be summarized descriptively using the Kaplan-Meier method. The 50th percentile of the Kaplan-Meier distribution will be used to estimate the median response duration.

Progression free survival will be defined as the time (in months) from enrollment to either first observation of progressive disease or occurrence of death due to any cause within 1 year (approximately 4 time intervals for disease assessments) of either first administration of tipifarnib or the last disease assessment. Similarly, survival will be defined as the time (in months) from enrollment to occurrence of death due to any cause within 1 year (approximately 4 time intervals for disease assessments) of either first administration of tipifarnib or the last disease assessment

Determination of RBC TI will be assessed by the Investigator through the review of subject transfusion requirements and hemoglobin levels. RBC TI will be defined as the absence of the intravenous infusion of any RBC transfusion during any consecutive "rolling" 56 days during the treatment period, i.e. days 1 to 56, days 2 to 57, days 3 to 58, etc. and a \geq 1 g/dL increase in hemoglobin level. The rise in the hemoglobin concentration in subjects who no longer require transfusions will be calculated as the difference between the maximum hemoglobin concentration and the minimum pre-transfusion value during the 12 weeks before enrollment in the study.

